3. OBJECTIVES AND ENDPOINTS

Data from Study VMDN-003-2 assessments at or prior to the Day 0, Day 104, and Day 180 Visits for Participants who enroll in Study VMDN-003-2b will be used as reference points for changes in efficacy parameters and for safety assessments during this extension study.

Objectives	Endpoints	
Primary		
To evaluate the efficacy of IM administration of Engensis on pain in participants with painful DPN in the feet and lower legs as compared to Placebo	Change in the means of the Average Daily Pain Scores (ADPSs) from the full Brief Pain Inventory for Diabetic Peripheral Neuropathy (BPI-DPN) from the 7 days prior to the Day 0 Visit (Study VMDN-003-2) to the 7 days prior to the Day 365 Visit in the intent-to-treat (ITT) population	
Secondary Efficacy:		
To evaluate the efficacy of IM administration of Engensis on the worst pain in Participants with painful DPN in the feet and lower legs as compared to Placebo	Change in the means of the Worst Pain scores from the full BPI-DPN from the 7 days prior to the Day 0 Visit (Study VMDN-003-2) to the 7 days prior to the Day 270 Visit and the 7 days prior to the Day 365 Visit for Engensis compared to Placebo	
To evaluate the efficacy of IM administration of Engensis on reducing pain in Participants with painful DPN in the feet and lower legs as compared to Placebo	 Proportion of Responders (≥ 50% reduction in the ADPSs from the full BPI-DPN) from the 7 days prior to the Day 0 Visit (Study VMDN-003-2) to the 7 days prior to the Day 270 Visit and the 7 days prior to the Day 365 Visit for Engensis compared to Placebo 	
Secondary Safety:		
To evaluate the safety of IM administration of Engensis in Participants with painful DPN in the feet and lower legs as compared to Placebo	Incidence of treatment-emergent adverse events (TEAEs) and treatment-emergent serious adverse events (TESAEs) for Engensis compared to Placebo Incidence of clinically significant laboratory values for Engensis compared to Placebo	

Version 1.0 27 Final: 11 Feb 2021

Tenamur co., Etc. Cort in Elivination vividiv-003-2

Objectives	Endpoints
	full BPI-DPN from the 7 days prior to the

Version 1.0 28 Final: 11 Feb 2021

Tenamin co., Etc. Com Delviere vindi cos 2

Objectives	Endpoints

Version 1.0 29 Final: 11 Feb 2021

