10.2 Baseline Definition

Unless specified otherwise, the baseline value for each variable is the value recorded at the last visit on or before start of dosing in Study VMDN-003-2.

For the pain scores from the BPI-DPN eDiary, the baseline value is the Average Daily Pain Score prior to the Day 0 visit from the main study.

Note that, for eligibility, the mean of Average Daily Pain Scores of the BPI-DPN eDiary should be ≥ 4 during the 7 days prior to Day 0. For the Average Daily Pain Score calculation, at least five (5) days need to have the available scores.

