12.6 Safety Analyses

Safety analyses in this study will evaluate the safety profile of Engensis as compared with control. No formal statistical testing will be conducted for the safety analyses. The following sections summarize the descriptive analysis methods for these safety endpoints. All participants in the Safety population will be included in these analyses. Participants will be grouped by treatment administered. All summaries will be derived based on available data in the extension study only. No imputation will be performed for missing values.

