12.6.2 Vital Signs

Vital signs and change from baseline will be summarized descriptively at each visit by treatment group. Additionally the number of subjects with the following vital signs of special interest will be summarized descriptively by treatment group:

- Systolic BP levels ≥ 180 mmHg
- Diastolic BP levels ≥ 100 mmHg
- Heart rate ≥ 180 beats/min
- Heart rate ≤ 60 beats/min

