12.6.3 HbA1c, Serum Chemistry, and Hematology

Central laboratory results will be summarized using International System (SI) of units. The laboratory results will be summarized by treatment and visit. The parameters within each panel are outlined in section 8.3.5.1 of the trial protocol, and lab panels for hematology and serum chemistry will be included.

Shift tables (i.e., low, normal, high at baseline versus low, normal, high at follow-up in a 3-by-3 contingency table) will be provided to assess changes in laboratory values from baseline to follow-up result at each scheduled follow-up visit. The counts and percentage of participants with each of the 9 possible “shift” outcomes will be calculated by treatment group. Individual laboratory data from scheduled and unscheduled visits will be listed.

Additionally the number of subjects with the following lab parameters of special interest will be summarized descriptively by treatment group:

- Glucose levels: critically high > 320 mg/dL (logic: 2-hour PP level for patients >60 years old is 160 mg/dl)
- Triglyceride levels: critically high \geq 500 mg/dL
- LDL cholesterol levels: critically high \geq 189 mg/dL
- Potassium levels: critically high \geq 5.5 mmol/L
- Hemoglobin levels: critically low \leq 6 g/dL
critically high \geq 20 g/dL
- WBC counts: critically low \leq 1,500/uL ($1.5 \times 10^9 / L$)
critically high \geq 20,000/uL ($20.0 \times 10^9 / L$)
- Platelet count: critically low \leq 50,000/uL ($50.0 \times 10^9 / L$)
critically high \geq 400,000/uL ($400.0 \times 10^9 / L$)
- Creatinine level: critically high \geq 2 mg/dL
- AST: critically high \geq 10 x ULN (upper limit of normal reference range)
- ALT: critically high \geq 10 x ULN (upper limit of normal reference range)
- Total bilirubin: critically high \geq 3 mg/dL

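### The special-interest laboratory and vital-sign tables (SAP 12.6.2, 12.6.3) count everyone beyond a limit in the extension, so they show prevalence and not new cases; a minor, free improvement

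*SAP*

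**What the plan says.** SAP 12.6.3 lists fixed laboratory limits and states: "Additionally the number of subjects with the following lab parameters of special interest will be summarized descriptively by treatment group". SAP 12.6.2 uses the same form for blood pressure and heart rate: "Additionally the number of subjects with the following vital signs of special interest will be summarized descriptively by treatment group". There are 18 limits in all, 4 for vital signs and 14 for laboratory values. Neither section sets a baseline condition or a denominator.

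SAP 12.6 sets the data window for all safety output: "All summaries will be derived based on available data in the extension study only". Yet SAP 10.2 defines a pre-dose reference, under which "the baseline value for each variable is the value recorded at the last visit on or before start of dosing in Study VMDN-003-2". Protocol section 3 says that main-study data at or before the Day 0, Day 104 and Day 180 visits "will be used as reference points for changes in efficacy parameters and for safety assessments during this extension study".

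The plan has other displays that refer to baseline. For laboratory values, "Shift tables (i.e., low, normal, high at baseline versus low, normal, high at follow-up in a 3-by-3 contingency table) will be provided", and individual values are listed. On which panels are displayed, SAP 12.6.3 says only that "lab panels for hematology and serum chemistry will be included". Vital signs get a change-from-baseline summary by visit, with no shift table.

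**The concern.** The secondary safety endpoints in both documents are framed as incidence on Engensis compared with Placebo, for adverse events and for clinically significant laboratory values. A count of everyone beyond a limit during the extension is a prevalence. It mixes new crossings with participants who were beyond the limit before they received anything.

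If carried-over cases are equally common in both arms, they add the same amount to each and pull the ratio towards 1. If they differ by chance between the arms, the difference can look like a drug effect or hide one. No formal safety testing is planned, so readers will judge these rows by comparing the counts. That makes the definition of a counted case matter.

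**Working it through.** **What can be reproduced.** Nothing. The documents give no sample size for the extension (SAP 8.1 leaves it to main-study completion and consent), no share beyond any limit at baseline, no persistence rate and no new-case rate. Every input below is an assumption.

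**Illustration 1: true ratio 3.** Let p be the share beyond the limit at baseline, the same in both arms (5% or 10%). Assume that 70% of them are beyond it again in the extension. Let q be the new-case rate among the rest: 2% v 6%, or 3% v 9%, Placebo v Engensis.

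- Counted rate = 0.70p + (1 - p)q
- Example, p = 5%, 2% v 6%: Placebo 0.035 + 0.95 × 0.02 = 0.054; Engensis 0.035 + 0.95 × 0.06 = 0.092; ratio 0.092 / 0.054 = 1.70
- Pooled carry-over share = 2 × 0.70p / (sum of the two counted rates); in the example 0.07 / 0.146 = 48%

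| p | New cases | Counted, Placebo | Counted, Engensis | Counted ratio | Counted v true difference (points) | Pooled carry-over share |
|---|---|---|---|---|---|---|
| 5% | 2% v 6% | 5.40% | 9.20% | 1.70 | 3.8 v 4.0 | 48% |
| 5% | 3% v 9% | 6.35% | 12.05% | 1.90 | 5.7 v 6.0 | 38% |
| 10% | 2% v 6% | 8.80% | 12.40% | 1.41 | 3.6 v 4.0 | 66% |
| 10% | 3% v 9% | 9.70% | 15.10% | 1.56 | 5.4 v 6.0 | 56% |

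The carry-over term cancels in the difference, leaving (1 - p)(q1 - q0). The absolute difference therefore falls by 5% or 10% of itself, while the ratio falls from 3 to 1.4-1.9.

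**Illustration 2: true ratio 2, from zero carry-over upwards.** Let r be the share of each arm beyond the limit both at baseline and in the extension. Counted rate = r + (1 - r) × new-case rate. With new cases 2% v 4%, the counted ratio is 2.00 at r = 0, 1.49 at r = 2%, 1.28 at r = 5% and 1.15 at r = 10%.

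Carry-over is the majority of counted cases only when r / (1 - r) exceeds the mean new-case rate of the two arms:

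- 1% v 2%: 0.015 / 1.015 = 1.5%
- 2% v 4%: 0.03 / 1.03 = 2.9%
- 5% v 10%: 0.075 / 1.075 = 7.0%

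What matters is carry-over relative to new cases. At r = 0.5% the counted ratio is 1.67 with 1% v 2%, but 1.91 with 5% v 10%.

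**What the other displays show.**

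- Shift tables use reference-range categories. A participant high at baseline who then crosses the special-interest limit stays in the high-to-high cell. A move from normal to high does not show whether the limit was crossed.
- Vital signs have change from baseline only, so a new fall to a heart rate of 60 or lower is not counted anywhere as new.
- Triglycerides and LDL are on the limit list, but the lipid profile is a separate panel in Protocol 8.3.5.1.5. SAP 12.6.3 names only hematology and chemistry, so lipid shift tables are not clearly planned.
- Listings give individual values, not an arm comparison.

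**The case against.** The strongest case against is that the endpoint already has a route that screens out stable disease. Protocol 8.3.5.1 leaves clinical significance to the Investigator and sets aside findings tied to the underlying disease unless they are more severe than expected. Protocol 10.2.1 makes clinically significant laboratory abnormalities, including those worsening from baseline, adverse events. SAP 12.6.1 limits adverse-event summaries to onset or worsening after Day 180. Grade 3 or 4 glucose and lipid disturbances are also adverse events of special interest (Protocol 8.4.5.2), with their own table. On this view the threshold rows are an extra display.

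Much of that stands. A reader might infer that these rows are the planned analysis of the laboratory incidence endpoint. Neither document says so, although the SAP names no separate table of Investigator-judged significant values. What the adverse-event route does not give is a count of new crossings of these particular limits, because it runs on clinical judgement and toxicity grade.

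A second objection also stands: about half of the 18 limits are extreme (for example AST or ALT at 10 × ULN or more, hemoglobin of 6 g/dL or lower, heart rate of 180 or more). Few participants would plausibly enter the study beyond them and stay there. Which limits mark chronic states is judgement, since the main-study eligibility criteria and baseline data are not in these documents.

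**Conclusion.** The point holds as a minor one. As written, the threshold tables show prevalence during the extension. Where a limit can mark a chronic state, the arm ratio may be diluted by an amount that the documents do not allow to be estimated. Under the assumptions shown, a true ratio of 3 reads as about 1.4-1.9 and the absolute difference loses only 5-10% of itself. For extreme limits with carry-over near zero, the effect is negligible. The shift tables, listings and adverse-event summaries cover part of the gap. They leave new crossings within the high or low category, new vital-sign crossings and possibly the lipids.

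A reader might go further and infer that most counted cases will be pre-existing. No rate in the documents supports that. In two of the four scenarios of Illustration 1 carry-over is a minority (38% and 48%). All of these tables are descriptive, so no test and no efficacy conclusion is affected.

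**What to change.** In SAP 12.6.2 and 12.6.3, for each limit:

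- Add the number and percentage newly beyond it, with the denominator being participants who have a value at the SAP 10.2 baseline that is not beyond the limit.
- Add the same count against the Day 180 value where one exists. The main-study laboratory schedule is not in these documents, so availability must be checked.
- Keep the present any-occurrence count and state its denominator.

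In SAP 12.6, state that main-study reference values are used despite the sentence restricting summaries to extension data. The planned change-from-baseline and shift tables already need this exception. Say also whether the lipid panel is included in the shift tables.

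The cost is SAP wording and extra table columns. The baseline values are already needed for planned output. The baseline comparison needs no new visits or data, and no limit changes.

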12.6.4 Retinal Fundoscopy

Retinal funduscopy findings in each eye (presence or absence of proliferative retinopathy, other finding) at screening (Baseline - Study VMDN-003-2) and the Day 365 visit and any changes from the baseline at the follow-up visits will be summarized descriptively by treatment group.

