- 2. Complete Physical Examinations will be performed on Days 270, 300, and 365/ET. The examination will include the following: head, eyes, ears, nose, and throat (HEENT); heart; lungs; abdomen; extremities; lymph nodes; neurological; and skin/integumentary systems. Any abnormalities should be categorized as clinically significant (CS) or not clinically significant (NCS), and the abnormalities should be recorded as adverse events using appropriate medical terminology.
- 3. **Retinal Fundoscopy** will be performed by an ophthalmologist up to 30 days before the Day 270 and 365 Visits (and, if possible, upon Early Termination if the Participant discontinues prior to the Day 365 Visit). Results of the fundoscopy examinations at the Day 270 and Day 365 Visits compared to results at the Day 180 Visit (Study VMDN-003-2) will be assessed by the Investigator.
- 4. 12-Lead Electrocardiogram (ECG) will be performed on Days 270 and 365/ET. The ECG recording and interpretation will be printed out and stored with the Participant's records. Any newly identified abnormalities are to be recorded as adverse events.
- 5. **Serum Chemistry, Hematology, and Lipid Profile:** These laboratory assessments will be evaluated on Days 270 and 365/ET.
 - Chemistry includes sodium, potassium, chloride, bicarbonate, calcium, inorganic phosphate, magnesium, glucose, amylase, lipase, creatine kinase, lactate dehydrogenase, and
 - o Kidney function tests (blood urea nitrogen, creatinine)
 - Liver function tests (aspartate aminotransferase [AST], alanine aminotransferase [ALT], alkaline phosphatase, gamma-glutamyl transpeptidase [GGT], total bilirubin, total protein, and albumin)
 - Hematology includes platelet count, hemoglobin, hematocrit, white blood cell count, and neutrophil
 count
 - Lipid Profile includes total cholesterol, high-density lipoprotein cholesterol (HDL-C), low-density lipoprotein cholesterol (LDL-C), and triglycerides
- **6. Urine Pregnancy Test:** Pregnancy tests for women of childbearing potential will be conducted in the clinic on Day 365/ET.

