8.4.5. Adverse Events of Special Interest

Categories of AESIs

There are three main categories of AESIs: 1) those considered to be related to the angiogenesis potential of Engensis, 2) other medical problems in this patient population, and 3) COVID-19 infections occurring in Participants during the study.

8.4.5.1. **AESIs Related to Angiogenesis**

Atherosclerosis

Hyperplasia of the vasa vasorum in the early stages of atherosclerosis is independent of angiogenesis, but the intimal neovascularization that follows the hyperplasia of the vasa vasorum

Version 1.0 42 Final: 11 Feb 2021

is angiogenesis-dependent.³⁵ Angiogenesis increases oxygen and nutrients to the artery wall and supports initial plaque growth. Once the atherosclerotic plaque develops, intimal angiogenesis is thought to contribute to characteristics of an unstable plaque, plaque hemorrhage, and plaque rupture. Therefore, diagnoses suggestive of recent coronary artery disease or cerebral vascular disease from the Day 180 Visit (VMDN-003-2) to the Day 365/ET Visit (VMDN-003-2b) will be evaluated as AESIs.

Proliferative diabetic retinopathy

Neovascularization is an advanced stage of diabetic retinopathy that is due to relentless abnormal fibrovascular proliferation.³⁶ Because the angiogenic potential of Engensis may promote the development of or stimulate abnormal fibrovascular proliferation in the retina, new fundoscopic changes or symptoms of proliferative diabetic retinopathy that occur from the Day 180 Visit (VMDN-003-2) to Day 365/ET (VMDN-003-2b) are considered AESIs.

Cancer

Angiogenesis plays an important role in the proliferation and metastatic spread of cancer as these processes are dependent on an adequate supply of oxygen and nutrients and removal of waste products.³⁷ All types of cancer reported between the Day 180 Visit (VMDN-003-2) to Day 365/ET (VMDN-003-2b) will be deemed to be AESIs.

Diabetes mellitus and obesity (BMI ≥30) each increases the risk of several types of cancer. ^{38,39} In type 2 DM, there is a 2- to 3-fold increased risk for pancreatic cancer, a 2-fold increased risk for hepatobiliary and endometrial cancers, a 50% increased incidence of colorectal cancer, and a 20% increased risk for breast cancer. ⁴⁰ Obese postmenopausal women have an increased risk of breast cancer, ⁴¹ and obesity is associated with a modestly increased risk of colorectal cancer, ^{42,43} pancreatic cancer, ⁴⁴ and prostate cancer. ⁴⁵

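### The SAP's fundoscopy summary has no Day 180 reference, so it cannot on its own show which proliferative retinopathy is new in the extension

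*SAP*

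**What the plan says.** **Protocol.** Footnote 3 of the Schedule of Activities (Section 1.3) schedules fundoscopy by an ophthalmologist for Day 270 and Day 365 and says that results "at the Day 270 and Day 365 Visits compared to results at the Day 180 Visit (Study VMDN-003-2) will be assessed by the Investigator". Section 8.4.5.1 then sets the event definition: "new fundoscopic changes or symptoms of proliferative diabetic retinopathy that occur from the Day 180 Visit (VMDN-003-2) to Day 365/ET (VMDN-003-2b) are considered AESIs". Section 3 is broader. It allows main-study data at or before Day 0, Day 104 and Day 180 to serve as reference points, for safety as well as efficacy.

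**SAP.** Section 12.6.4 tabulates "presence or absence of proliferative retinopathy, other finding" in each eye, and takes these findings "at screening (Baseline - Study VMDN-003-2) and the Day 365 visit and any changes from the baseline at the follow-up visits". This follows the general rule in Section 10.2, under which "the baseline value for each variable is the value recorded at the last visit on or before start of dosing in Study VMDN-003-2" unless something else is specified. No Day 180 fundoscopy result enters the summary.

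Two other SAP rules bear on the point. Section 12.6.1 starts the treatment-emergent window on the day after the Day 180 visit and tabulates AESIs by preferred term. The opening of Section 12.6 says: "All summaries will be derived based on available data in the extension study only". Section 6.1, which lists changes from the protocol, does not mention the fundoscopy reference.

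**The concern.** The extension exists to assess durability and long-term safety after dosing has ended, and proliferative retinopathy is one of the angiogenesis-related risks that the protocol names. Table 1 in protocol Section 2.3.1 lists eye disorders among the risks of Engensis and cites the Day 270 and Day 365 fundoscopy as mitigation. It also notes that diabetic retinopathy was seen more often on placebo in earlier work. The same section records a vitreous hemorrhage in a previous trial that was classed as possibly related.

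The scheduled ophthalmologist examination is the one source that looks at participants systematically, whether or not anyone reports an event. If its only specified summary runs from Screening, a reader cannot tell from it whether an eye became positive while the main study was running or after Day 180. The AESI table uses the Day 180 origin, but it depends on findings having been recognised and reported as events. Nothing in the specified output lets the one be checked against the other.

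**Working it through.** Neither document gives a retinopathy rate, and safety is descriptive, so there is no planned figure to reproduce. The check is a comparison of texts followed by an enumeration.

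**1. Reference points side by side**

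| Place | Reference | Follow-up |
|---|---|---|
| Protocol 1.3, footnote 3 | Day 180 | Day 270, Day 365 |
| Protocol 8.4.5.1 (AESI) | Day 180 | to Day 365/ET |
| SAP 12.6.1 (TEAEs, AESIs) | Day 180 visit date + 1 | extension |
| SAP 12.6.4 (fundoscopy) | main-study Screening | Day 365, and changes at follow-up visits |

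The fundoscopy summary is the only one of the four that does not start from Day 180.

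**2. What a Screening-to-Day 365 table can hold.** Code each eye 0 (proliferative retinopathy absent) or 1 (present) at Screening, Day 180 and Day 365. Three binary time points give 2 × 2 × 2 = 8 patterns. The Screening-by-Day 365 table has 2 × 2 = 4 cells, so each cell pools two patterns:

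| Screening → Day 365 | Patterns pooled (Screening-Day 180-Day 365) |
|---|---|
| absent → absent | 0-0-0 and 0-1-0 |
| absent → present | 0-0-1 and 0-1-1 |
| present → absent | 1-0-0 and 1-1-0 |
| present → present | 1-0-1 and 1-1-1 |

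Let X be the number of eyes in the absent-to-present cell. Then

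new since Day 180 within that cell = X − (number of 0-1-1 eyes).

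The 0-1-1 count is not reported and can be anything from 0 to X, so the number new since Day 180 can also be anything from 0 to X.

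**3. Does Day 270 resolve it?** SAP 12.6.4 covers changes at follow-up visits, so Day 270 changes from Screening are arguably included. An eye positive at Day 270 may already have been positive at Day 180, so the same pooling occurs. Only an eye negative at Day 270 and positive at Day 365 could be identified as new in the extension, and only if the two visits were cross-tabulated by eye. The SAP does not specify that.

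**4. With Day 180 as reference.** The Day 180-absent, Day 365-present cell holds exactly 0-0-1 and 1-0-1: eyes positive at Day 365 that were not positive at Day 180. Eyes already positive at Day 180 (0-1-1 and 1-1-1) fall in a different cell. The ambiguity in step 2 goes away.

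**The case against.** The strongest reply is that the two documents describe different activities and both can be followed. The footnote's Day 180 comparison is an Investigator's assessment, not a specified table, and protocol 9.3.4 sets no reference for a fundoscopy summary. Protocol Section 3 permits a pre-dose reference, and there is good reason to want one: all injections fell between Day 0 and Day 104, so a Day 180 reference alone would hide retinopathy that arose soon after dosing. All of this stands. It is why the Screening summary should be kept and why this is not a breach of the protocol.

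A second reply is that new retinopathy is already handled as an AESI, counted from the day after Day 180, with blinded Medical Monitors assigning each event to a category. This also stands. A reader might infer from SAP 12.6.4 that the plan as a whole cannot distinguish onset before Day 180 from onset after it. The documents do not support that inference, because SAP 12.6.1 makes the distinction for reported events. The limitation belongs to the examination table alone.

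A reader might also infer that the fundoscopy table and the AESI counts are bound to conflict. That does not follow either. One counts findings per eye, including other findings; the other counts participants with reported events, including symptoms, over a different window. They may differ without either being wrong, and need not match exactly even after the fix.

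What these replies leave untouched is that no specified output shows, from the scheduled examinations, what changed between Day 180 and Day 365.

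**Conclusion.** The point holds as a gap in one descriptive table. SAP 12.6.4 uses a permitted reference, but it leaves out the one that the protocol's footnote and AESI definition use, and SAP 6.1 does not say that this was a choice. The size is the 0-to-X range: the absent-to-present cell puts no lower bound above zero on the number of eyes new in the extension, and no upper bound below the whole cell. No rate can be attached, because the documents give none.

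There is also a small inconsistency within the SAP. Read literally, the extension-only rule in Section 12.6 would exclude the Screening values that Section 12.6.4 needs.

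The conclusion assumes that Day 180 fundoscopy results exist in the main-study data, which the footnote presupposes. No hypothesis test is affected, since no formal safety testing is planned. The priority is low: a cheap improvement rather than a necessary correction.

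**What to change.** In SAP 12.6.4:

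- Add shifts from Day 180 to Day 270 and from Day 180 to Day 365, by treatment group. Present them per eye and per participant, counting a participant as new if either eye is new. Show missing examinations as their own category, since SAP 12.6 rules out imputation.
- Keep the Screening-referenced summary and label it as the 12-month change.
- State that Screening and Day 180 values are carried in from the main study as reference values, as an exception to the extension-only rule in SAP 12.6.
- Note in SAP 6.1 how the two references relate to footnote 3 of the Schedule of Activities.

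The cost is one more descriptive table. If the Day 180 results exist as the footnote presupposes, nothing new has to be collected, and no error rate or clinical procedure changes.
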